Evaluation of an Interactive Text-Message Based Brief Intervention to Reduce Substance-Impaired Driving among College Students

NCT03496129

04/03/2018

Study Goals:

The overarching goal is to reduce driving after drinking, drug use, and combined drug/alcohol use among college students.

We will conduct a 3-group trial with 150 college students (project 50% female and 20% minority) recruited from a large public university.

Group 1: substance information only

Group 2: substance-impaired driving personalized feedback only

Group 3: substance impaired driving personalized feedback and MI interactive text messages

Aim 1: Evaluate a text based substance-impaired driving intervention in a Randomized Clinical Trial.

Hypothesis 1: Groups 2 and 3 will report greater reductions in driving after substance use at 3-month follow-up compared to Group 1.

Aim 2: Determine whether interactive text-messages sustain intervention effects over time.

Hypothesis 2: Group 3 will report greater reductions in driving after substance use at 6-month and 12-month follow-up compared to Group 2.

Procedures:

Eligibility Criteria

Inclusion Criteria:

- o Age 18 or older
- Currently enrolled (full or part-time) in college
- Ability to speak, read, and write in English
- Reports driving after drinking two or more drinks prior to driving at least three times in the past three months AND/OR reports driving after using marijuana or any other substance prior to driving at least three times in the past three months
- Reports having access to a motor vehicle, a valid driver's license, and plans to drive a vehicle in the next 3 months
- Reports access to a cell phone and willingness to read intervention material and exchange 3 texts post intervention with the study administrator
- Reports a valid email address

• Exclusion Criteria:

Currently in treatment for substance use or abuse

Approximately 500 students will be recruited from Western Kentucky University (WKU) through the WKU subject pool, emails sent to undergraduate courses, and flyers posted around the Western Kentucky University campus. We expect 150 students to participate in the clinical trial.

Screening:

Approximately 500 college students (recruited through the Western Kentucky University subject pool, emails sent to undergraduate courses, and flyers posted around the Western Kentucky University campus) will complete a brief (10-15 minute) screening survey via the SONA system or through email to identify those students who might be eligible to participate in this study. Students 18 years or older with current access to a motor vehicle who report driving within two hours of drinking two or more drinks at least three times in the past three months AND/OR driving within two hours of using marijuana or any other substance at least three times in the past three months will be eligible to participate in this trial. If the participant meets eligibility criteria, the researcher will contact the participant, explain the project procedures and confidentiality, and will invite the participant to participate in further phases of the study.

Students who meet inclusion criteria as per the screener completed through the WKU Studyboard System or those who meet inclusion criteria as indicated on screeners emailed to classes will be contacted by a study administrator to confirm eligibility status. Other interested university students will be instructed via flyers to contact the Substance Abuse Intervention Lab by email or text and a study administrator will send them a link to the screener. Determination of eligibility status will include a short questionnaire regarding inclusion and exclusion criteria. For all participants, eligibility status and study description will occur via a phone call giving participants the opportunity to ask questions. Furthermore, this phone call will serve as an "instruction" session in which study details are explained and participants have a chance to ask questions about the study. We will also make sure the participants understand the consent process at this time and review the study consent form, which they will subsequently complete online. Participants will be informed that the study is designed to learn more about college students' lifestyle and health behaviors, particularly drug and alcohol use and driving attitudes and behaviors, and that the study will involve random assignment to a single mobile-based session, along with three brief mobile-based follow-ups.

After completing all screening procedures, eligible and interested individuals will be sent a baseline questionnaire via text-message to be completed remotely on mobile phone via a secure web survey. All self-report measures will be completed via mobile phone on a secure, web-based survey. Prior to completing baseline measures via mobile phone, participants will be provided with a consent form and will be informed of the study's purpose, risks, benefits, compensation, and all other pertinent study details. Participants will be provided with a phone number and email address should they have questions and will also be informed in the consent that they can discontinue the study at any time. If participants do not choose to "accept" the conditions of the consent form or decide not to participate in the study at any time, they will be provided with an informational document containing details about driving under the influence and a list of mental health resources in the community. This remote, web-based session will last

approximately 1 hour and, following the completion of the online consent form, will include an assessment battery (approximately 30 minutes) and either a) a personalized feedback intervention, b) a personalized feedback intervention + interactive text messaging with an interventionist, or c) a substance information intervention (control group). Participants in the personalized feedback intervention + interactive text messaging condition will receive 3 interactive text messages to facilitate processing of the intervention material and goal setting. Upon completion, participants will be thanked for their participation via text message and a 3-month follow-up assessment will be scheduled. Following completion, students will be awarded 1 hour of credit for participation, which the researcher will grant through the Studyboard System. Alternatively, students may elect to receive a payment of \$20 in the form of an Amazon gift card for participation.

Though we will not be able to encrypt text messages, all messages will be sent from a secure mobile phone and we will inform all participants that we cannot guarantee the privacy of these messages prior to signing study consent. The phones and email addresses we use will be password protected and kept in a secure locked room accessible only to research staff.

Three-months, 6-months, and 12-months post intervention, participants will be asked to complete a mobile-based follow-up self-report assessment battery. The follow-up will assess the impact of the interventions on substance-impaired driving attitudes and behaviors. For each follow-up, participants will be sent the link (by mobile phone) to an identical assessment battery. These sessions will last approximately 30 minutes. Upon completion, participants will be thanked for their participation via text message and participants will be awarded 30 minutes of credits for participation, which the researcher will grant through the Studyboard System. Alternatively, students may elect to receive a \$15 Amazon gift card for participation.

Interventions.

Substance Impaired-Driving Personalized Feedback Intervention. Following the baseline assessment, participants will be sent a link via text message to a secure website containing substance-impaired driving specific personalized feedback. Feedback will include the following elements: a personalized substance use profile and substance-impaired driving profile, information on social norms related to substance use and substance-impaired driving, personalized information on BAC (or level of impairment due to drug use) prior to driving, costs associated with a DUI citation in Kentucky, and information on combined drug and alcohol impaired driving risk (if endorsed). The goals of this session are to raise concern about potential consequences relating to driving after substance use and to correct faulty normative perceptions of substance use and substance-impaired driving. Participants will be instructed to view the personalized feedback document and to respond to a number of questions embedded in the feedback document as a comprehension and fidelity check.

Substance Impaired-Driving Personalized Feedback plus Interactive Text Messaging Intervention. Following the baseline assessment, participants will be sent a link via text message to a secure website containing substance-impaired driving specific personalized feedback (described above). Participants will be asked to send a text

message back to the study administrator after viewing the feedback document. After confirming receipt and processing of the document, the study administrator will then send the participant three text messages containing the following open-ended questions: 1) Of the information you just viewed, what was most interesting?, 2) How would receiving a DUI impact your future career goals?, and 3) What is your plan for driving after substance use in the future? Based on participant responses to these open-ended questions, the interventionist will send follow-up text messages to provide appropriate reflection/encouragement in Motivational Interviewing (MI) style. All interventionists will be trained in MI and a clinical psychologist with expertise in MI will supervise the text messaging interactions. The interactive texts are expected to enhance intervention retention/processing and to provide an interpersonal/interactive element that may enhance efficacy (Walters et al., 2009).

Information Condition. Students randomized to the information condition will receive standard information about alcohol and other drugs and substance-impaired driving via a link to a website delivered through text message. The informational document provided will detail information about how alcohol, drugs, and combining alcohol and other drugs affects the brain and nervous system, memory, and driving performance, and is similar to substance education programs commonly found on college campuses. The substance-related information will not be personalized. Students will be provided the opportunity to ask any questions related to the information provided via interactive text message.

Research Measures

We will apply for a Certificate of Confidentiality and inform participants during recruitment that their data will remain confidential in order to enhance the accuracy of participants' self-reports. We will also ensure that study administrators receive training on conveying a nonjudgmental attitude toward reports of substance use. All assessment measures will be collected via a secure web-based survey that will be given at baseline, and 3, 6, and 12 months post-intervention.

Demographics Form. These questions will ask about participant gender, age, ethnicity, past and present academic status and grade point average, and fraternity/sorority affiliation.

Drug Use Questionnaire (DUQ; Hien, & First, 1991). This measure will be used to assess the frequency of past month illicit and prescription drug use.

Daily Drinking Questionnaire (DDQ; Collins, Parks, & Marlatt, 1985). The DDQ will be used to assess information regarding past month typical drinking frequency and quantity, as well as the number of heavy drinking episodes (5 or more drinks for a male participant, 4 or more drinks for a female participant) in the past month. Heavy drinking episodes among college students are related to numerous public health concerns including risky sexual behavior, accidents, injury, and death.

Impaired Driving Questions: Participants will be asked 10 questions related to driving after consuming alcohol and/or other drugs.

Brief Young Adult Alcohol Consequences Questionnaire (BYAACQ; Kahler et al., 2008). The B-YAACQ is a 24-item self-report measure that assesses whether or not participants have experienced items on a list of 24 potential alcohol-related problems. Participants indicate whether they have experienced each alcohol-related problem by circling 'yes' or 'no' for each item. The items are then summed for a total score. The BYAACQ has demonstrated high internal consistency with college students as well as good reliability and validity (Kahler et al., 2008).

Marijuana Problems Scale (MPS; Stephens, Roffman, & Curtin, 2000). The MPS assesses different types of problems experienced as a result of smoking marijuana or using other drugs in the past year. Individuals respond to 20 items on a three-point scale (0=No Problem, 1=Minor Problem, 2=Serious Problem). Higher MPS scores indicated greater drug-related problem severity.

Data Analyses.

Power. A power analysis for a design with three conditions being measured on four occasions was run using the G-Power software (Buchner et al., 1997). Based on a previous Murphy et al. (2010) study examining Al driving outcomes among students receiving a BI or education control intervention and the review of behavior change interventions delivered by mobile telephone short-message service (Fjeldsoe, 2009), we chose to utilize an anticipated between-groups effect of .58, which was the mean of the effect size found with alcohol-impaired driving outcomes (d=.42) and mobile delivered behavior change interventions (d=.73). This would require 44 participants per condition total to have a power of .80, assuming α = .05. In order to achieve this sample size at follow-up, we plan to enroll 50 participants per condition, allowing for some attrition.

Overall Evaluation of the Aims. The primary study analyses will examine whether there is a statistically significant difference between treatment groups in change in self-reported substance impaired driving. Repeated measures mixed modeling analyses will be conducted to compare the brief intervention groups and the informational control group on each of the primary outcome variables at 3-month, 6-month, and 12-month follow up. Mixed modeling examines data similarly to repeated measures ANOVA; however, mixed modeling provides increased flexibility in handling missing data by utilizing all available data for each participant and provides ease of adaptation for multiple research designs (Hox, 2010). For each model tested, one of the primary outcome variables will serve as the dependent variable with gender, age, and ethnicity included as covariates.

Hypotheses and Specific Data Analysis Plan

Aim 1: Evaluate a Text Based Substance-Impaired Driving Intervention in a Randomized Clinical Trial

Hypothesis 1: Groups 2 and 3 will report greater reductions in driving after substance use at 3-month follow-up compared to Group 1.

Aim 1 analytic plan. To evaluate hypothesis 1, generalized linear mixed models (GLMM) will be utilized, which represent an extension of linear mixed models to non-normal data. GLMM with a negative binomial distribution, which allows for over-dispersion in count outcomes, will be utilized for outcomes of non-normally distributed count data (i.e., total number of times driving after drinking, using drugs, and/or combining alcohol and drugs). For each model tested, one of the primary outcome variables (number of times driving after drinking, using drugs, and combined use of alcohol and drugs) as the dependent variable with gender, ethnicity, and age included as covariates.

Aim 2: Determine whether interactive text-messages sustain intervention effects over time.

Hypothesis 2: Group 3 will report greater reductions in driving after substance use at 6-month and 12-month follow-up compared to Group 2.

Aim 2 analytic plan. To evaluate hypothesis 2, generalized linear mixed models (GLMM), which represent an extension of linear mixed models to non-normal data, will be utilized. GLMM with a negative binomial distribution, which allows for over-dispersion in count outcomes, will be utilized for outcomes of non-normally distributed count data (i.e., total number of times driving after drinking, using drugs, and/or combining alcohol and drugs). For each model tested, one of the primary outcome variables (number of times driving after drinking, using drugs, and combined use of alcohol and drugs) as the dependent variable with gender, ethnicity, and age included as covariates.

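### The Aim 1 and Aim 2 models do not condition on the baseline impaired-driving count; adding it would be a cheap and usually modest gain in precision, not the repair of an error

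*Combined protocol and SAP*

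**What the plan says.** Under Data Analyses, the Aim 1 and Aim 2 analytic plans both specify a negative binomial GLMM with one impaired-driving count "as the dependent variable with gender, ethnicity, and age included as covariates". The Overall Evaluation of the Aims gives the same list: "with gender, age, and ethnicity included as covariates". Neither aim's plan states the arm, time and arm-by-time terms or which occasions form the outcome.

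Baseline data exist. Research Measures says that the battery is "given at baseline, and 3, 6, and 12 months post-intervention", and within it "Participants will be asked 10 questions related to driving after consuming alcohol and/or other drugs".

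The wording on how baseline enters the model points two ways:

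- Towards baseline as an outcome occasion: the primary analysis concerns a "difference between treatment groups in change in self-reported substance impaired driving"; the text explains that "Mixed modeling examines data similarly to repeated measures ANOVA"; the Power paragraph describes "a design with three conditions being measured on four occasions"; and both hypotheses are about reductions.
- Towards follow-up only: the groups are to be compared "on each of the primary outcome variables at 3-month, 6-month, and 12-month follow up", with baseline not named.

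The first reading is the likelier one.

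**The concern.** In a randomised trial with a repeated count outcome, the baseline value of that count is usually the strongest available predictor of follow-up. Here it costs nothing to obtain, yet it is missing from a list that does include gender, age and ethnicity. Three models fit the text: follow-up counts only, baseline as an outcome with arm-specific means (a change contrast), and baseline as an outcome with a mean common to the arms. All are legitimate under randomisation, but they differ in interval width and in the estimate that a given sample yields. At stake is precision with about 44 analysed participants per arm. A secondary benefit of fixing the model now is that nobody has to choose among the three after seeing the data.

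**Working it through.** **1. The plan's own figure.** The Power paragraph gives d = .58, α = .05, power .80 and 44 per condition. The 44 is reproduced by a one-way F test of three equal groups with Groups 2 and 3 both .58 from Group 1: f = .58 × √2 / 3 = .2734, power .8002 at 44 per group. The documents do not state this pattern; it was found by trying variants. It takes no credit for baseline, so any gain from adjustment comes on top of the stated power.

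**2. Linear approximation.** The correlation ρ is not in the documents; .3, .5 and .7 are assumed. With equal variances at baseline and follow-up, the relative variance of the arm contrast is:

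- follow-up only: 1
- change with arm-specific baseline means: 2(1 − ρ) = 1.40, 1.00, .60
- baseline as covariate: 1 − ρ² = .91, .75, .51

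The covariate saves 9, 25 and 49% against follow-up only, and 35, 25 and 15% against change (for example 1 − .91/1.40 = 35%). It saves nothing against a model that already uses a common baseline mean.

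**3. Effect of the eligibility floor.** Entry requires at least three episodes in three months for alcohol and/or for drugs. If that truncates the baseline count, baseline varies less than follow-up. With k the ratio of baseline to follow-up SD, the change contrast has variance 1 + k² − 2ρk. Restricting simulated log(count+1) to baseline counts of three or more gave ρ = .278, .476, .683 and k = .638, .685, .739. At the first setting the change variance is 1 + .407 − .355 = 1.052 and the adjusted variance is 1 − .077 = .923, a saving of 12.3%. The other two settings give 5.4% and .6%.

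**4. Simulation of the planned model type.** Negative binomial GLMM, two arms of 44, baseline and three follow-ups, 3-month contrast, 1,000 trials per cell. Assumed: population mean count 6, rate ratio .6, random-intercept variance .49/.73/.93 and dispersion .67/.31/.07 for nominal correlations .3/.5/.7. Scenario (a) has no floor. In (b) everyone has a baseline count of three or more. In (c) half the participants qualify on the other substance and have mean .5 on this outcome. Savings are 1 minus the ratio of empirical variances.

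| Scenario, nominal ρ | Follow-up only | Baseline covariate | Change, arm-specific | Saving vs follow-up only | Saving vs change |
|---|---|---|---|---|---|
| (a) .3 | .0632 | .0557 | .0832 | 11.9% | 33.1% |
| (a) .5 | .0667 | .0477 | .0577 | 28.5% | 17.3% |
| (a) .7 | .0633 | .0279 | .0291 | 55.9% | 4.1% |
| (b) .3 | .0576 | .0525 | .0599 | 8.9% | 12.4% |
| (b) .5 | .0495 | .0378 | .0390 | 23.6% | 3.1% |
| (b) .7 | .0382 | .0201 | .0192 | 47.4% | −4.7% |
| (c) .3 | .1970 | .1046 | .1153 | 46.9% | 9.3% |
| (c) .5 | .1859 | .0695 | .0682 | 62.6% | −1.9% |
| (c) .7 | .1657 | .0449 | .0409 | 72.9% | −9.8% |

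Achieved within-arm correlations of log(count+1) were .29/.51/.69 in (a), .27/.46/.66 in (b) and .65/.76/.83 in (c). Each variance has a relative Monte Carlo error of about √(2/999) = 4.5%, so differences of a few per cent are not distinguishable from zero.

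**5. Sensitivity.** A second GLMM simulation (600 trials per cell) gave savings against change of about 29/17/6% without a floor and 12/2/−6% with one. When eligibility was set by a separate screening count, the savings were mostly positive, about 5 to 34% at 3 or 12 months. The worst loss, in the mixed-qualifier scenario, was about 9%. A simpler check with one follow-up and a marginal (GEE) change contrast gave larger savings under the floor (26 to 38%), but that is not the planned model and is not relied on.

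**6. Common baseline mean under the floor, scenario (b).** The mean model-based variance was .0456, .0314 and .0176 against empirical variances of .0512, .0373 and .0194, ratios of .89, .84 and .91. Coverage of 95% intervals was .932, .927 and .939 (Monte Carlo error about .007). The covariate model covered .958, .952 and .951.

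**The case against.** The strongest case against is that, on the likelier reading, nothing is missing: the analysis of change over four occasions already uses baseline, and choosing between two valid ways of using it is partly preference. The two scenarios that reflect the three-episode rule, (b) and (c), give savings of 12% at best and losses in three of six cells. A rerun of (b) with a different optimiser gave about 8, 1 and 0%, with nominal coverage for the arm-specific model (.952/.958/.944). The covariate version also drops participants with no follow-up, although the plan values using all available data and allows for a fall from 50 to 44 per arm. The simulations used complete data, so that cost is unmeasured.

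Most of this stands, and it limits the point to a modest one. It does not remove it. The floor is checked at screening rather than on the baseline battery, the combined-use count has no floor of its own, and with a separate screening count the savings were mostly positive. The text also still permits a follow-up-only model, against which the saving is substantial.

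A reader might infer three stronger claims, none of which the documents support:

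- **That baseline was forgotten.** The references to change and to four occasions indicate otherwise.
- **That the trial is underpowered.** In the linear approximation, a change contrast at ρ = .3 would have omnibus power of .648 rather than .800 at 44 per group. But the documents give neither ρ nor the SD unit of the .58, and under the floor the change variance at low correlation is about 1.05, not 1.40.
- **That a large gain is there for the taking.** The large figures require a follow-up-only model, which is the less likely reading.

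**Conclusion.** The point holds as a precision-only improvement worth making, with medium confidence. Against the likelier arm-specific change contrast, the covariate saves from about 30% of the variance at low correlation to nil, or loses up to about 10%, at high correlation. The range is about 12% to −6% if the floor binds on the baseline count itself. In interval width, a 30% saving is a narrowing of 1 − √.70 = 16%, a 12% saving is 1 − √.88 = 6%, and a 10% loss is a widening of √1.10 − 1 = 5%. If baseline would otherwise be unused, the saving is roughly 10 to 50%, and more (47 to 73% in scenario c) for outcomes on which many participants have low counts.

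Only the 44 per arm, the four occasions and the three-episode rule come from the documents. The correlation, mean count, dispersion, rate ratio, the scenario (c) mix and the application of a screening rule to the baseline count are assumptions.

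**What to change.** In each Aim 1 and Aim 2 GLMM, state that the outcomes are the 3-, 6- and 12-month counts, with arm, time and arm-by-time terms. Keep gender, age and ethnicity, and add the baseline count of the same outcome as a covariate, for example log(count+1). Read Hypothesis 1 from the 3-month contrasts and Hypothesis 2 from the 6- and 12-month contrasts. Do not enter the same baseline value as both outcome and covariate.

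If the ordinary group-by-time model with arm-specific baseline means is intended instead, it is valid and the plan should say so. A model with a common baseline mean should be used only with robust or bootstrap standard errors, because it under-covered when eligibility truncated the baseline counts.

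The cost is one or two sentences in each analytic plan and no new data. The downsides are that a functional form for baseline must be chosen in advance, participants with no follow-up contribute no rows, and a small loss of precision is possible at high correlation.
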